Implementation of onsite, rapid ART initiation among People Who Inject Drugs living with HIV at Syringe Services Program

Protocol Version 2

Protocol Version Date 4/25/22

eProst ID Number 20200793

PI [name]

NCT Number NCT04650269

- 1) **Protocol Title:** Implementation of onsite, rapid ART initiation among People Who Inject Drugs (PWID) living with HIV at Syringe Services Program (SSP)

- 2) **Objectives***

Aim 1: To evaluate/assess the effectiveness and feasibility of same-day rapid initiation of ART for PWID living with HIV who utilize the SSP (*SSP Rapid Initiation*).

Aim 2: To identify barriers to success of HIV care retention and treatment adherence among PWID preparing for entry into long-term HIV care.

Aim 3: To compare adherence of patients in *SSP Rapid Initiation* after transition to a traditional healthcare clinic.

- 3) **Background***

PWID experience extensive barriers to engagement in HIV care. Challenges in linkage to care, retention in care, and viral suppression in PWID are well documented, with estimates that less than half of PWID living with HIV in the U.S. are virally suppressed^{5,6}. In the 2018 Miami outbreak investigation and public health response in PWID, we were able to support 100% of newly infected individuals in achieving viral suppression through a test-and-treat approach with intensive patient navigation and medication management; but faced challenges in initiating ART in previously diagnosed PWID, with only 53% achieving suppression. Reasons for this sub-optimal result could include recognized barriers to HIV care and retention within the Miami community, including drug use, mental illness, stigma and transportation issues^{7,8}. Although Miller et al.⁹ recently reported that intensive and flexible patient navigation with psychosocial counseling was central to increased initiation of ART and viral suppression, the literature on evidence-based approaches to initiation of ART and retention in care for PWID is lacking.

Why Test and Treat? Early HIV diagnosis and immediate ART initiation are essential to rapidly decrease viral load, reduce the impact of outbreaks, and improve quality of life among PWID^{10,11,12}. Established Test and Treat paradigms have shown decreased time to virologic suppression, the ultimate goal of controlling HIV transmission among PWID and their sexual partners¹³. However, traditional healthcare systems may not be the ideal environment to initiate HIV care in PWID, a population so stigmatized by the healthcare system and society at-large that they often avoid care due to profound distrust and structural barriers. ART initiation at an SSP is potentially an ideal venue, bringing services to the patient and making healthcare easily accessible. With SSPs just beginning in Florida, an *SSP Rapid Initiation* approach developed at the Miami IDEA SSP will enable new programs to rapidly implement pathways to rapid ART initiation.

- 4) **Inclusion and Exclusion Criteria***

[figure not shown]
- 1) Adult (age>18 years); 2) positive rapid HIV test; 3) ability to provide informed consent; 4) HIV RNA > 200; 5) creatinine clearance > 30 as measured by serum creatinine; 6) no allergy to bictegravir/emtricitabine/tenofovir alafenamide (BFTAF) as indicated by patient history and self-reported allergies. *Any other comorbidities that at the discretion of the investigator would prevent the participant from participating in the study.*

5) Study Design

We plan to utilize a hybrid quasi-experimental design to test the effectiveness and implementation outcomes of successful delivery of rapid ART initiation intervention in an SSP (Figure 1). In addition, we will use a multi-method approach, collecting both quantitative and qualitative data on patients (n=50) accepting the rapid ART initiation protocol at the SSP, patients declining to engage in the rapid ART initiation protocol, and patients after transition to a traditional Ryan White clinic. To assess the effectiveness of the *SSP Rapid Initiation*, we will compare the percentage of PWID virally suppressed at 6 months post baseline at the SSP compared to at 6 months post transition to UM/Jackson Adult Outpatient HIV Clinic. Since this proposed study is in its pilot phase, this study will not be examining differential effects in treatment groups in the study, but rather provide preliminary data to support a future randomized-controlled trial. Represented in the figure below, participants at the SSP will be tested for HIV using a rapid test, which when reactive will be confirmed using a second rapid HIV test from another manufacturer following a CDC-approved dual rapid HIV testing algorithm. If a patient tests positive, the patient will be offered immediate initiation onto ART at the SSP. Baseline labs (4th Generation HIV test, HIV viral load, CD4, HIV genotype, CBC, CMP, Gonorrhea/Chlamydia, RPR, HCV Antibody, HCV RNA, HbsAg, HBsAb, HAV Total) will be obtained and sent to the Miami-Dade County Health Department. Patients will have up to 7 days post HIV-positive test to start on ART (per definition of rapid ART initiation). The community advisory board and peer navigators at the SSP will assist in the *SSP Rapid Initiation* protocol design, execution, and process improvement. Peers will work between the SSP and the Ryan White clinics. Our experience with the 2018 HIV cluster in PWID in Miami taught us that medication management (i.e., pill lockers at the SSP, third party pickup of ART at ADAP by SSP staff, weekly medication drops to participants unable to access medications at the fixed site) was highly effective at supporting adherence in PWID living with HIV. Peer navigators will conduct outreach to *SSP Rapid Initiation* participants, monitor appointments, and provide transport to healthcare services. This intensive linkage and active follow-up delivered by peer PWID living with HIV is essential to delivery of care to this population. Peers will be tasked with helping participants with eligibility (e.g., Ryan White, Medicaid) and ADAP enrollment when they transition to the transitional HIV clinic. This grant will enable them to have ongoing support in clinic after transition to the traditional healthcare environment for long-term care.

Patients who decline engagement in ART after one week will be asked to partake in semi-structured interviews. Patients who accept will be initiated onto ART at the SSP. A medication adherence plan will be developed for each patient by SSP staff to optimize medication adherence. Quantitative and qualitative assessments exploring barriers and facilitators of HIV treatment adherence will be given at 1, 3, 6 and 12 months post treatment start date. In addition, HIV viral load will be measured at 1, 3, 6, 9 and 12 months post treatment start date to assess viral suppression.

Figure 1. Conceptual Framework of *SSP Rapid Initiation* Pilot Study

Quantitative Assessments of those accepting rapid ART

Baseline assessment of participants will include socio-demographics, drug and sexual risk behaviors, HIV knowledge, and SSP utilization. If re-engaging: date of HIV diagnosis, previous HIV clinic attendance, previous ART exposure, and reason(s) for discontinuing ART. Follow-up assessments will include a side effect inventory, mental health screening, timeline follow-back on ART adherence, timeline follow-back on drug use.

Qualitative Assessment of those accepting rapid ART

Qualitative assessments will include patient perspectives on HIV diagnosis and living with HIV, including both HIV and PWID stigma. The interviews will explore which symptoms are most important to the patient, their experience with ART in the past and experience on BFTAF in the current study, and facilitators and barriers to ART adherence in the past and in the current study. These assessments will also include formative feedback on ART initiation at the SSP, medication management at the SSP, follow-up HIV care at the SSP, and barriers and facilitators to transition to a more traditional HIV clinic for long-term care. Those who are eligible for the study will be consented and asked to participate in a 30-minute interview conducted at the IDEA SSP for which they will receive \$50

Qualitative Assessment of those declining rapid ART

In-depth interviews with PWID living with HIV who do not engage in treatment with 7 days of HIV test result will be conducted. We anticipate conducting 10 interviews, which is sufficient to achieve data saturation and will be conducted within 3 months post HIV test result. Inclusion criteria are: 1) 18 years of age or older; 2) enrolled in the IDEA SSP; 3) HIV positive rapid test result; 4) English or Spanish speaking, 5) declined rapid ART initiation at the SSP. Those who are eligible for the study will be consented and asked to participate in a 30-minute interview conducted at the IDEA SSP for which they will receive \$25.

These semi-structured interviews will explore: 1) the role of key personal and structural barriers to engagement in HIV care (e.g., transportation, poverty, and stigma); 2) perceived benefit of engaging in rapid initiation of HIV care on personal health outcomes (i.e., viral

suppression); 3) reasons for declining rapid ART initiation protocol (e.g., prior clinic experience, previous ART side effects), 4) recommendations for structuring the intervention to maximize participant engagement (e.g., physical location, hours of operation, duration, and frequency); 5) recommendations for intervention facilitator demographics and training; and 6) current knowledge, attitudes, and awareness regarding HIV treatment in PWID. All interviews will be audio-recorded and transcribed verbatim by an external transcription company.

6) Arms and Interventions

This single arm pilot study will assess the effectiveness of on site initiation of HIV care and followup at an SSP (fixed site or mobile exchange on outreach). The study is 1 year duration, and study visits are conducted at 0, 1, 3, 6, 9 and 12 months as outlined above. The intervention is delivery of HIV care outside of a traditional healthcare clinic. The medication offered will be BFTAF, 50/200/25mg tablet to be administered orally. The intervention will include wraparound support by the peer navigator. Study visits will be conducted either at the IDEA Exchange fixed location, or on the mobile unit in the community (e.g. homeless encampments). The fixed site and mobile unit are equipped with private rooms for medical encounters. Medical visit with a provider and phlebotomy will be provided on site.

7) Procedures Involved*

	Screening	0	1	3	6	9	12
Lab Assessments	HIV Rapid	HIV Ag/Ab Test HIV RNA CD4 count HIV genotype CBC CMP GC/CT RPR HCV Ab HCV RNA HBsAg anti-HBs Anti-HAV Total	HIV RNA CD4 count CBC CMP GC/CT RPR	HIV RNA CD4 CBC CMP GC/CT RPR	HIV RNA CD4 CBC CMP GC/CT RPR	HIV RNA CD4 CBC CMP GC/CT RPR	HIV RNA CD4 CBC CMP GC/CT RPR
Assessments	Eligibility	Baseline		Quant/Qual	Quant/Qual		Quant/Qual

Participants at the SSP will be tested for HIV using a rapid test, which when reactive will be confirmed using a second rapid HIV test from another manufacturer following a CDC-approved dual rapid HIV testing algorithm. Confirmatory testing no longer requires venipuncture. A 4th generation test will be sent as indicated below. The initiation of care, however, will not be delayed. If a patient tests positive on dual rapids, the patient will be offered immediate initiation onto ART at the SSP. If accepted, they will provide informed consent. They will have an immediate HIV care visit with a provider in person or via encrypted Zoom technology. A prescription for BFTAF will be written and filed for the participant, and BFTAF will be provided on site. ART will be initiated immediately, and in the rare case that changes in dosing or ART based on lab values (e.g. creatinine) is needed,

they will made once lab results return. This is now standard of care nationwide for rapid initiation. The care visit will be documented in UChart. Baseline labs (4th Generation HIV test, HIV viral load, CD4, HIV genotype, CBC, CMP, Gonorrhea/Chlamydia, RPR, HCV Antibody, HCV RNA) will be obtained and sent to the Miami-Dade County Health Department. Patients will have up to 7 days post HIV-positive test to start on ART (per definition of rapid ART initiation).

Peer navigators will conduct outreach to *SSP Rapid Initiation* participants, monitor appointments, and provide transport to healthcare services. This intensive linkage and active follow-up delivered by peer PWID living with HIV is essential to delivery of care to this population. A medication adherence plan will be developed for each patient by SSP staff to optimize medication adherence. Quantitative and qualitative assessments exploring barriers and facilitators of HIV treatment adherence will be given at 1, 3 and 6 months post treatment start date. In addition, HIV viral load will be measured at 1, 3, and 6 months post treatment start date to assess viral suppression. Peers will be tasked with helping participants with eligibility (e.g., Ryan White, Medicaid) and ADAP enrollment when they transition out of the trial to a traditional care environment.

For each 30-minute interview conducted at the IDEA SSP, participants will receive \$50.

Qualitative Assessment of those declining rapid ART

In-depth interviews with PWID living with HIV who do not engage in treatment with 7 days of HIV test result will be conducted. We anticipate conducting 10 interviews, which is sufficient to achieve data saturation and will be conducted within 3 months post HIV test result. Participants will be consented and asked to participate in a 30-minute interview conducted at the IDEA SSP for which they will receive \$25.

8) Primary Endpoints

Study Aim	Primary Outcome (Patient-Level)	Definition	Primary Outcome (Implementation)	Definition
Aim 1	Viral Suppression	HIV viral load <200 copies/ml at 6 months post baseline	Acceptability of Rapid Initiation of ART	Number and percentage of PWID living with HIV that enter SSP Rapid Initiation
Aim 2	Treatment Adherence	HIV Viral Load <200, pill counts, medication log, appointment attendance	Barriers to Adherence	Exploration of challenges to HIV treatment management at SSP
Aim 3	Viral Suppression	HIV Viral Load <200, pill counts, medication log, appointment attendance	Feasibility of peer navigation	Exploration of challenges to HIV treatment management at traditional HIV clinic

For this proposed study, we expect that ongoing, peer-driven patient navigation based at the SSP will result in patients' remaining virally suppressed after transition to the UM/Jackson Adult Outpatient HIV Clinic. More importantly, based on the hybrid design, this study will lay the foundational groundwork to provide a proof of concept for HIV care at SSPs, including pertinent implementation information for future expansion sites in the state of Florida. We expect to uncover barriers and facilitators to implementation of rapid ART initiation at an SSP, including patient-level perspectives on improving delivery of care developed in the *SSP Rapid Initiation among PWID Living with HIV* protocol.

Secondary outcomes: Time to viral suppression, or viral suppression at 1 month, will be assessed. Treatment adherence will be assessed both by follow-up viral load results (1, 3, 6, 9, 12 months) as well as by medication management measures (e.g., PWID accessing meds weekly, pill counting by SSP staff) and attendance at clinic visits. Successful transition to HIV care at a Ryan White clinic will also be assessed. The clinic-based peer patient navigator will assist in transition of patients to long-term care within six months of ART initiation. Ryan White clinic appointment attendance and successful re-enrollment in Ryan White/ADAP will be assessed.

9) Data and Specimen Banking*

For clinical data, we will use the UHealth's electronic health record, UChart, which is locked under dual authentication.

All data collected will be housed in the REDCap database system, which is locked under dual authentication by University of Miami Information Technology and then extracted for analysis by the principal investigator. Only study staff will have access to survey results.

As for the in-depth interviews, sessions will be audio-recorded, transcribed by an external company, de-identified for analysis and stored on a password-protected computer in a secured office in the Don Soffer Clinical Research Center. Only study staff will have access to results.

10) Data Management*

Quantitative Data Analysis: Quantitative data will be analyzed using descriptive statistics and frequencies to present pilot data on rapid ART initiation at an SSP. Data will be presented as frequency tables, and viral suppression will be reported as a percentage suppressed at each time-point (1, 3, 6, 9, 12 months). All quantitative data will be stored and managed in REDCap and all analyses will be performed using SAS statistical software (Version 9.4; SAS Institute, Cary, NC). Categorical data will be analyzed using frequency of responses and continuous variables will be analyzed using means and standard deviations.

Qualitative Data Analysis: Qualitative data collected from the in-depth interviews will be analyzed using general inductive methodology³¹, which allows for themes to be developed from the raw data based on a study objective/research question. A data codebook will be generated in an iterative process during transcript reading by the study team. All qualitative data analysis will be conducted using Dedoose (version 8.2.14, Sociocultural Research Consultants, Los Angeles, CA), a cross-platform software used for analyzing qualitative and mixed methods research.

11) Risks to Subjects*

Study procedures: there is risk of discomfort to phlebotomy, but no risk above routine HIV care

Study Drug: Serious risks of taking BFTAF includes serious drug reactions such as lactic acidosis, hepatomegaly with steatosis, hepatotoxicity, hepatitis B virus exacerbation, pancreatitis, nephrotoxicity, neutropenia, immune reconstitution syndrome, autoimmune disorders, suicidality, and angioedema. Common adverse reactions include diarrhea, headache, fatigue, hyperbilirubinemia, elevated CK, abnormal dreams, dizziness, insomnia, hypercholesterolemia, hyperamylasemia, neutropenia, LFTs elevated, nausea/vomiting, depression, rash, dyspepsia, abdominal pain, asthenia, increased creatinine, bone density loss, arthralgia/myalgia, cough, paresthesia, peripheral neuropathy, palmar-plantar hyperpigmentation, hypertriglyceridemia, hematuria, hyperglycemia, glycosuria, rhinitis and flatulence.

12) Adverse Events and Serious Adverse Events

AEs will be any of the common adverse reactions defined above. SAEs will include any hospitalization or death or disability that occurs with participants in the trial. AEs will be reported to the IRB in continuing reviews. SAEs will be reported to the IRB within 24 hours.

13) Potential Benefits to Subjects*

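### The mental health screen, drug-use timeline follow-back and side effect inventory are listed only at follow-up, so early losses have no mental health value and symptoms have no pre-treatment reference

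*Combined protocol and SAP*

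**What the plan says.** Section 5 (Study Design), under the quantitative assessments of those accepting rapid ART, gives two lists. For visit 0: "Baseline assessment of participants will include socio-demographics, drug and sexual risk behaviors, HIV knowledge, and SSP utilization". Participants re-engaging in care also give their diagnosis, clinic and ART history. For later visits: "Follow-up assessments will include a side effect inventory, mental health screening, timeline follow-back on ART adherence, timeline follow-back on drug use".

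The start of the later assessments is described in more than one way. Section 5 says: "Quantitative and qualitative assessments exploring barriers and facilitators of HIV treatment adherence will be given at 1, 3, 6 and 12 months". The text of section 7 (Procedures Involved) says they "will be given at 1, 3 and 6 months post treatment start date". The schedule table in section 7, as extracted, shows a baseline assessment at month 0, nothing at month 1, and the first combined quantitative and qualitative assessment at month 3.

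Section 2 (Objectives) sets the aim that these data serve: "Aim 2: To identify barriers to success of HIV care retention and treatment adherence among PWID preparing for entry into long-term HIV care". The aim names no particular barrier. Section 3 (Background) does, when it explains poor suppression among previously diagnosed people: "including drug use, mental illness, stigma and transportation issues".

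Section 11 (Risks to Subjects) lists common BFTAF reactions, among them "abnormal dreams, dizziness, insomnia", and also depression, nausea and fatigue. Section 12 counts any reaction on that list as an adverse event and does not mention the participant's state before treatment. Section 10 (Data Management) plans descriptive statistics only.

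**The concern.** Retention is part of what Aim 2 is meant to explain. Someone who disappears before the first follow-up assessment is a retention failure, and is also the person for whom the mental health screen and the drug-use timeline follow-back are never completed at a scheduled visit. Whether the value is missing then depends on the outcome. Frequency tables of these barriers would describe people who stayed, while the pilot is meant to inform a later randomised trial in which early loss will matter.

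The side effect inventory raises a separate problem. Several listed reactions are symptoms that a person can have before taking any ART. In a single-arm study the participant's own state at day 0 is the only within-study comparator, and for symptoms the plan does not list its collection.

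**Working it through.** The protocol has no figure to reproduce: it states no attrition rate, no symptom rate and no statistical basis for the sample size. The check is a comparison of what is listed at each visit.

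**Step 1. Instruments by visit (section 5).**

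- Mental health screen: not listed at visit 0; listed at follow-up.
- Side effect inventory: not listed at visit 0; listed at follow-up.
- Drug use: a risk-behaviour item at visit 0; timeline follow-back at follow-up only.
- ART adherence timeline follow-back: follow-up only. This is not at issue, since adherence to study ART does not exist before ART starts.

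Of the two Background barriers considered here, mental illness has no baseline measure. Drug use has one, but not the measure used later, so baseline and follow-up cannot be compared on the same scale.

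**Step 2. Length of the gap.**

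- Section 5 text: months 1, 3, 6 and 12, so the first value comes at 1 month.
- Section 7 text: months 1, 3 and 6, so again 1 month.
- Section 7 table as extracted: months 3, 6 and 12, so 3 months.

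The table may have been damaged in extraction, so the 3-month reading is uncertain. The two text lists also differ from each other on month 12.

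**Step 3. How many people could lack a value.** Inputs: N = 50 (section 18, Local Number of Subjects) and an assumed proportion *a* lost before the first follow-up assessment. The number without a mental health value or a drug-use timeline is N × *a*; the number described is N × (1 − *a*).

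- *a* = 10%: 50 × 0.10 = 5 without, 45 described.
- *a* = 20%: 50 × 0.20 = 10 without, 40 described.
- *a* = 30%: 50 × 0.30 = 15 without, 35 described.

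Those without these values would still have the baseline drug risk-behaviour item.

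**Step 4. Symptoms.** If the inventory asks only whether a symptom is present, the reported frequency is the sum of two groups: those whose symptom was present before ART and persists, and those in whom it is new. Without a day-0 value the two cannot be separated. The baseline blood count and metabolic panel in the section 7 table give a reference for laboratory reactions, but not for insomnia, depression, nausea or fatigue. No symptom rate is given, so no size can be computed.

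**The case against.** The case on the other side is substantial, and parts of it stand.

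- **A reader might infer that Aim 2 has no data on two of its own named barriers.** The documents do not support that. Aim 2 names no barrier, and drug behaviours are asked about at baseline. Only mental health is wholly unmeasured there.
- **A reader might infer that a barrier could never be shown to precede poor adherence.** That is too strong. The first assessment, at month 1 or month 3, comes before the 6-month primary viral load. Timeline follow-back is retrospective, and its look-back window is not stated.
- **A reader might infer that side effect rates will be inflated.** The wording of the inventory is not given, and it might ask about onset or change. What stands is that inflation is possible. Side effect frequency is not a listed primary or secondary outcome.
- **Aim 2 concerns people preparing for long-term care, so early losses may lie outside it.** That reading is open. But the aim also names retention, which is hard to study only among those retained.
- **The analysis is descriptive and promises no estimate linking barriers to loss.** This is correct, and with 5 to 15 losses such an estimate would be very imprecise even with day-0 data. It does not change who the descriptive tables cover. The interviews, and the recorded reasons for stopping earlier ART, add some information on barriers.
- **Missing a study visit does not make a person unreachable.** Recruits are regular programme users and peers do outreach, so some missing values might be recovered. A late value would still not be a pre-treatment value.
- **The lists need not be exhaustive, and Figure 1 is not available here.** This limits certainty, but nothing in the available text places these instruments at visit 0.

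**Conclusion.** The point holds in a limited form. As written, no mental health screen and no symptom inventory are listed before ART, and drug use lacks the baseline counterpart of its follow-up measure. The mental health and drug-use timeline results would therefore describe people retained to the first follow-up assessment, at month 1 or month 3 depending on which part of the protocol governs. Pre-existing symptoms can be counted as side effects.

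The size of both effects is unknown. The figure of 5 to 15 of 50 participants rests wholly on an assumed early loss of 10% to 30%, and no figure is offered for symptoms. The conclusion also assumes that the section 5 lists are complete. The consequence is for interpretation: whom Aim 2 describes and how side effects are read. No planned test changes, and the 6-month viral suppression endpoint is untouched. This is a cheap improvement to a pilot, not a flaw that undermines it.

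**What to change.** - Add the same mental health screen, drug-use timeline follow-back and symptom inventory to visit 0, with the existing baseline questionnaire. They can follow the care visit so that ART is not delayed, provided that the symptom inventory refers to the pre-dose state.
- In the analysis section, describe the visit-0 values separately for participants retained and lost at the first follow-up assessment.
- Report a symptom as emergent only if it is new or worse than at day 0, and state this beside the adverse event definition.
- Reconcile the assessment months in the section 5 text, the section 7 text and the section 7 table.

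The instruments and the visit already exist, so the cost is mainly a longer first visit, on a day that already holds testing, consent, a provider visit, a full laboratory panel and the start of ART. A mental health screen on the day of a positive test may also partly reflect acute distress; the report should say so when it presents the visit-0 values.

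### The Section 7 narrative stops viral loads and assessments at month 6 and has participants leave the trial at transition, against the 12-month schedule elsewhere in the plan; only the month-1 assessment is truly unsettled

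*Combined protocol and SAP*

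**What the plan says.** Section 7 (Procedures Involved) contains both a table and a narrative. The narrative states that "HIV viral load will be measured at 1, 3, and 6 months post treatment start date to assess viral suppression" and that the quantitative and qualitative assessments "will be given at 1, 3 and 6 months post treatment start date". It then says that peers help with eligibility and enrollment "when they transition out of the trial to a traditional care environment".

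Section 5 (Study Design) says that the same assessments "will be given at 1, 3, 6 and 12 months post treatment start date" and puts viral load at months 1, 3, 6, 9 and 12. It plans quantitative and qualitative data on those accepting rapid ART, "patients declining to engage in the rapid ART initiation protocol, and patients after transition to a traditional Ryan White clinic". It also says of suppression that "we will compare the percentage of PWID virally suppressed at 6 months post baseline at the SSP"; the other side of that comparison is suppression six months after the move to the outpatient HIV clinic.

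Section 6 sets a one-year study with visits at months 0, 1, 3, 6, 9 and 12. The Section 7 table shows HIV RNA at each of those visits, and quantitative/qualitative assessments at months 3, 6 and 12 with months 1 and 9 blank. Section 8 (secondary outcomes) and Section 10 (quantitative analysis) both list viral load at 1, 3, 6, 9 and 12 months. Section 8 expects transition to long-term care no later than six months after ART is started.

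**The concern.** Staff who run visits are likely to work from the procedures section, and its narrative gives a shorter study than the rest of the document. It drops the month-9 and month-12 viral loads and the month-12 assessment, and its wording on transition can be read as the end of participation.

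Aim 3 is about what happens after participants move to the traditional clinic. With transition expected by month 6, month 12 is the only assessment that falls after the move for every participant who keeps to that plan, and it is the one the narrative omits. A visit that is not made on time cannot be recovered later.

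**Working it through.** The plan states no figure to reproduce here. The check sets the schedules side by side and counts what falls after transition.

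**Schedules as written (months after ART start)**

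| Source | Viral load | Quant/qual assessments |
|---|---|---|
| Section 5 | 1, 3, 6, 9, 12 | 1, 3, 6, 12 |
| Section 7 table | 1, 3, 6, 9, 12 | 3, 6, 12 |
| Section 7 narrative | 1, 3, 6 | 1, 3, 6 |
| Section 8, secondary outcomes | 1, 3, 6, 9, 12 | not listed |
| Section 10, quantitative analysis | 1, 3, 6, 9, 12 | not listed |

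Section 6 names no viral load, but its visit schedule matches the longer list. The table's assessment row has seven cells for seven columns (Screening, 0, 1, 3, 6, 9, 12), so the alignment looks sound.

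- Viral load: four statements give five months and one gives three. The narrative is alone.
- Month-12 assessment: Section 5 and the table include it, and Section 6 has a visit then. The narrative is again alone.
- Month-1 assessment: Section 5 and the Section 7 narrative include it; the table leaves it blank. Nothing else decides it.

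**Scheduled data after transition.** Let transition occur at month t, with 0 < t ≤ 6 (Section 8). Count the scheduled months strictly later than t.

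| | t = 1 | t = 3 | t = 6 |
|---|---|---|---|
| Assessments, narrative {1, 3, 6} | 2 | 1 | 0 |
| Assessments, Section 5 {1, 3, 6, 12} | 3 | 2 | 1 |
| Assessments, table {3, 6, 12} | 3 | 2 | 1 |
| Viral loads, narrative {1, 3, 6} | 2 | 1 | 0 |
| Viral loads, full {1, 3, 6, 9, 12} | 4 | 3 | 2 |

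Section 5 and the table give the same assessment counts, so the open month-1 question does not change what is seen after transition at these times.

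**The 6-months-post-transition target.** It falls at month t + 6, which is later than month 6 for every t > 0. The narrative's last viral load is at month 6, so it has none at or after the target, whenever transition happens.

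**Upper bounds with 50 participants, if the narrative is followed.** Viral loads omitted: 2 × 50 = 100. Month-12 assessments omitted: 1 × 50 = 50.

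**Aim 1.** Its viral suppression outcome is at month 6, which is in both schedules.

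**The case against.** The strongest reply is that the document already answers the question. The short schedule appears in one narrative and is contradicted by the table in the same section and by four other sections. The transition phrase sits in a sentence about peers' enrollment tasks, not about follow-up, and the matching sentence in Section 5 speaks only of moving to the HIV clinic. The study is a descriptive pilot with no statistical basis for its sample size. Most of this stands. It limits the harm to the case where staff follow the narrative, but it does not make the narrative correct.

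A reader might infer more than the documents support:

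- That no assessment schedule prevails. For month 12 one does; only month 1 is open.
- That Aim 3 would have no data for a participant who moves at month 6. What would be missing is the scheduled assessments and viral loads. Section 8 also assesses Ryan White appointment attendance and re-enrollment, and Section 5 plans data after transition without tying them to particular months.
- That a blank month-1 assessment damages the month-1 suppression outcome. That outcome is a laboratory value, and the table draws HIV RNA at month 1. A same-visit adherence report would be useful, but nothing in the plan requires it.
- That follow-up does end at transition. One phrase suggests so, while Sections 5, 6, 8 and 10 plan later data. The Section 5 statement "This grant will enable them to have ongoing support in clinic after transition to the traditional healthcare environment for long-term care" is weak evidence either way, since support in clinic does not by itself show continued trial participation.

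**Conclusion.** The Section 7 narrative is wrong as written, in its two schedules and in its transition phrase. The 12-month schedule prevails elsewhere. If the narrative is followed, a participant who moves at month 6 loses one scheduled assessment and two viral loads, leaving none after transition. If it is not followed, nothing is lost. The Aim 1 month-6 outcome is unaffected either way. Whether month 1 carries an assessment needs a decision from the sponsor.

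The importance is minor to should-fix: the correction is small and protects Aim 3, but the intended schedule can mostly be recovered from the rest of the document. The conclusion assumes transition by month 6, as Section 8 expects, and the table's columns as extracted; without the table, Section 5 still contradicts the narrative on month 12. The documents do not show which text the site follows.

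Which draw should serve as the 6-months-post-transition value is a separate question of endpoint definition and is not part of this point.

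**What to change.** In the Section 7 narrative:

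1. Give viral load at 1, 3, 6, 9 and 12 months.
2. Add month 12 to the quantitative and qualitative assessments.
3. Replace the transition phrase with a statement that participants move to the traditional HIV clinic and that study follow-up continues to month 12.

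Separately, the sponsor should confirm whether month 1 has an assessment, then align the table cell and both narratives with that answer.

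**Cost.** The wording changes are two sentences, one phrase and, if month 1 is kept, one table cell. They add no visit and no viral load beyond those in Sections 5, 6, 8 and 10. If the site now follows the narrative, restoring the month-12 assessment costs up to 50 × $50 = $2,500 in participant payments and 50 × 0.5 h = 25 hours of interviews, plus external transcription and staff time, for which the documents give no rate. Section 5 and the table already imply this work. The same amounts apply to month 1 if the site now follows the table and the sponsor keeps that assessment.
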